#### **Objectives**

#### **Overall objectives**

Objective 1: To determine whether differential activation in a priori brain regions of interest (ROI) to selected reward and inhibition probes can predict drug use during active treatment.

Hypothesis 1a: Greater activation of a priori limbic ROI (e.g., interconnected amygdala/ventral striatal cluster during brief drug cues; bilateral ventral striatum during reward risk) prior to (FMRI 1) and during (FMRI 2) active treatment will predict greater drug use during the active treatment phase.

Hypothesis 1b. Lower activation of a priori prefrontal inhibitory ROI (e.g., lateral orbitofrontal cortex; supragenual anterior cingulate) during affect-congruent Go-NoGo; inhibition of cue-triggered craving) prior to (FMRI 1) and during (FMRI 2) active treatment will predict greater drug use during the active treatment phase. Objective 2: To determine whether differential activation in a priori brain ROI to selected reward and inhibition probes can predict relapse following active treatment.

Hypothesis 2a: Greater activation of a priori limbic reward ROI (e.g., interconnected amygdala /ventral striatal cluster during brief drug cues; bilateral ventral striatum during reward risk during brief drug cues; reward risk) prior to (FMRI 1), and following (FMRI 3) active treatment will predict greater drug use during the 12-week follow-up period.

Hypothesis 2b: Lower activation of a priori prefrontal inhibitory ROI (e.g., lateral orbitofrontal cortex; supragenual anterior cingulate) during affect-congruent Go-NoGo; inhibition of cue-triggered craving) prior to (FMRI 1) and following (FMRI 3) active treatment will predict greater drug use during the 12 week follow- up period.

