#### Primary outcome variable(s)

For Objective 1: The primary drug use outcome for this objective is illicit-positive urines during the 12 weeks of active treatment (2 Urine Drug Screens per week; 20 total) after FMRI 2.

For Objective 2: The primary drug use outcome for this objective is illicit-positive urines during the 12-week follow-up period (weekly urines; 12 total) after FMRI 3.

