#### Design

The proposed project will use functional magnetic resonance imaging (fMRI) and specific probes of reward and inhibition as biomarkers predicting drug use during and after treatment in 216 patients addicted to cocaine, marijuana, and prescription opioids. Participants will be scanned before, during, and after 12 weeks of active treatment specific to each of these drugs of abuse. The brain fMRI measures will be correlated with the primary clinical outcome of drug use (by urine drug screen) during the treatment and follow-up phase. An exploratory objective will examine the impact of genetic (e.g., polymorphisms modulating reward and inhibition) and epigenetic factors (e.g., history of prior trauma/ abuse) on the relapse-relevant brain measures. (Genetics are now collected under the [name] for The Genetics of Addiction Study approved by Penn IRB for the entire Treatment Research Center that has it own separate protocol (#811705) and consent).

The main strengths of the project are:

 The Treatment Research Center places a value on direct benefit to the patients participating in our research. Substance-specific pharmacological and/or psychosocial interventions are provided by certified and trained professionals. Using trained providers for the behavioral baseline treatment also reduces sources of variance extraneous to the brain predictors, giving us the best chance to determine their predictive ability.
 Inclusion of three pharmacologically distinct substances of abuse will provide robust and generalizable data on the brain predictors of relapse.

3) Using a single scanner will eliminate problems inherent to large multi-center studies that rely on more than one imaging facility, such as data incompatibility across scanner platforms.

All participants: Following successful screening, all participants will participate in the fMRI 1 and 2 sessions. Next, cocaine participants will receive a behavioral intervention (Coping with Craving), marijuana participants will be randomized (double-blind), to either baclofen or placebo and prescription opiate participants will receive naltrexone. After 2 weeks of treatment patients will participate in fMRI 3. Prior to and following each probe, craving and withdrawal will be assessed. Participants will participate in fMRI 4 at the end of Treatment. Participants will return weekly for 12 weeks during the follow up period.

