#### Screening Procedures: [All Procedures are done for Research Purposes]

1. Urine drug screens (UDS) Urine drug screens for the target drug (using standard cut-offs), will be the primary outcome measure. These will be obtained twice weekly during the 12- week active treatment period, and once weekly during the 12-week follow-up period. They will be processed as part of the VA collaboration. A 10-panel dipstick urine drug screen and a urine pregnancy test (females) will be done prior to each naltrexone injection for prescription opiate participants during the first 3 treatment months and may be done once a month during follow-up as well or if the VA is able to add the 2 additional tests (buprenorphine and oxyContin) to their urine drug screen then the VA option may be used during follow-up. Also, a 10-panel dipstick urine drug screen will be done once for all the studies as part of the screening process. For prescription opiate participants additional 10-panel dipstick urine drug screens may be done for detox, encouragement and safety reasons.

2. Sexually-transmitted infections/HIV testing. Our addicted patients are at high risk for HIV, both through drug-related activity (sharing crack pipes), and through unprotected sexual activity occasionally in the context of drug use. Our brain variables (hyperresponse to the promise of reward; poor inhibition of impulses toward drug and sexual reward) would be expected to predict these secondary outcomes. We will test for HIV at baseline and at 24-week follow- up.

3. Genetics. Blood samples for DNA analysis will be obtained from each participant during initial screening. [name] lab will provide the genetic analysis. Genomic DNA will be extracted from anticoagulated venous blood samples using a standard salting out method [96]. Genotyping of the DRD4, DAT VNTR and OPRM1 will be performed using standard methods as described previously [97-99]. DRD2 and COMT genotypes will be determined using the Applied Biosystems Inc. (ABI) Assays-on-demand (ABI, Foster City, CA, USA) SNP genotyping assay as per manufacturers protocol. Genotyping quality control steps for all markers will include Hardy-Weinberg equilibrium determination and genotyping of 20% duplicates for each marker. (Collected under [name] IRB approved genetic protocol #811705.)

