Procedures that apply to all 3 studies: A complete psychiatric and medical examination with routine laboratory tests will be performed to ensure that participants have no medical illnesses that would keep you from participating in the study. If the participant comes to us from a residential setting such as, Gaudenzia, Inc. and has had the required medical examination and routine laboratory tests within the last 30 days these may suffice and with the participants permission will be requested/released to us for our records. About 4 tablespoons of blood will be drawn for laboratory tests. For Marijuana participants who are HIV+ and participate in the study an additional tablespoon of blood will be collected to check for CD4 counts. Participants who have a CD4 count that is 200 or less will not be eligible to participate. Participants will undergo a series of interviews and be required to fill out research forms that allow the doctors working on the study to get basic information concerning drug use, medical history, and mood state. The initial screening procedures will last approximately 3.5 hours. An x-ray may be needed to determine eligibility. This screening process may be done over 2 days depending on nurse and therapist schedules.

For cocaine participants their present physical status, vital signs and a uring pregnancy test will be reassessed prior to theirr admission to Presbyterian Hospital. A breathalyzer test will also be done.

The results of the initial screening procedures, after participants sign informed consent, will determine whether they can enter the study. Included in this are a medical screening with a physical, a psychological screening, an electrocardiogram, a urine pregnancy test (females), the Edinburgh Handedness Scale and the Addiction Severity Index.

If participants are found to be eligible after the initial screening additional assessments and Neurobehavioral Tasks will be done, which take about 2 hours to complete part at baseline (12 minutes), part at week 12 (43 minutes) and most of the tasks are repeated after scan day 1 (1 hour and 35 minutes).

Next participants will be scheduled for their first and second fMRI scan sessions and first psychosocial treatment appointment or medication appointment. After 3 weeks of psychosocial treatment and/or medication, a third fMRI will take place (2 weeks for prescription opiates). After week twelve treatment will stop, and participants will undergo a fourth fMRI once treatment ends.

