#### **Analysis Plan**

Objective 1: To determine whether differential activation in a priori brain regions of interest (ROI) to selected reward and inhibition probes can predict drug use during active treatment.

For hypothesis 1a, the two brain predictors will be the extracted signal change in the interconnected left amygdala-striatal cluster during the Brief Drug Cues task, and the extracted signal change in the bilateral ventral

striatum in the Balloon Analog Risk Task. For Hypothesis 1b, the predictors will be based on the left amygdala for the Go-NoGO contrast in the Affect-congruent Go-NoGo task, and the dorsal anterior cingulate in the Craving Inhibition task. These measures will be obtained from the fMRI 1 and fMRI 2 scans.

The four brain responses will be analyzed in a similar way. In each case, the responses will be the repeated urine screens obtained during the last ten weeks of treatment. These urine results will be binary, indicating either cocaine use, opiate use, or marijuana use, since the previous test. For each of hypotheses 1a and 1b, we will use mixed effects logistic regression (McCulloch et al, 2008) to relate variation in these responses to a measure of brain activation occurring during one of four tasks. We anticipate that using a random intercept will be sufficient to take account of within-subject correlations across the time points, although more complex covariance structures will be examined. As we are interested in assessing the separate effects of each brain region on the responses, our main analyses will consider the brain regions separately, so Hypotheses 1a and 1b will be addressed by four separate models, with the treatment urines as responses, and one brain predictor as an explanatory variable. These models will be estimated for the fMRI 1 and fMRI 3 scans.

The primary hypotheses will be addressed by the point estimates and tests of significance associated with the regression coefficients for the brain predictors in these analyses. In further analyses, we will examine the joint effects of the brain predictors for the different regions in the same model, and will use model selection based on information criteria (BIC) to determine the simplest model that provides a good fit to the data.

Objective 2: To determine whether differential activation in a priori brain ROI to selected reward and inhibition probes can predict relapse following active treatment.

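### The on-treatment scan is timed at 2 weeks in one section and at 3 weeks for cocaine and marijuana in another; the Objective 1 outcome window fits only the 2-week timing

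*Combined protocol and SAP*

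**What the plan says.** Two sections time the on-treatment scan differently. The Design section says, for all participants: "After 2 weeks of treatment patients will participate in fMRI 3". The paragraph on procedures common to all three studies (under Imaging Assessments) says: "After 3 weeks of psychosocial treatment and/or medication, a third fMRI will take place (2 weeks for prescription opiates". Both sections number four scans, with the third during treatment, so they describe the same scan.

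The Objective 1 outcome is stated twice. Primary outcome variable(s) gives "illicit-positive urines during the 12 weeks of active treatment (2 Urine Drug Screens per week; 20 total) after FMRI 2". The Analysis Plan says "the responses will be the repeated urine screens obtained during the last ten weeks of treatment", with no distinction between cohorts, and reads each result as "indicating either cocaine use, opiate use, or marijuana use, since the previous test". Screening Procedures gives the frequency: "These will be obtained twice weekly during the 12- week active treatment period".

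On the predictor side, the Objectives section numbers three scans and states hypotheses on activation "prior to (FMRI 1) and during (FMRI 2) active treatment will predict greater drug use during the active treatment phase". The Analysis Plan first takes the Objective 1 brain measures from fMRI 1 and fMRI 2, then says "These models will be estimated for the fMRI 1 and fMRI 3 scans".

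**The concern.** Objective 1 asks whether a scan predicts later drug use. For the on-treatment scan, this requires every response to come after the scan. The outcome definition meets that requirement with a scan after 2 weeks but not with a scan after 3 weeks. On the 3-week schedule, the week-3 urines of cocaine and marijuana patients would be modelled as predicted by a scan not yet done, while the prescription opiate cohort would have no such urines. One coefficient would then combine two temporal designs, and the stated count of 20 could not be reached in two of the three cohorts. If this stays open, the choice of window could be made after the data are seen.

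**Working it through.** **Inputs**
- Treatment length 12 weeks, two urines a week (Screening Procedures): 24 in all.
- Scan after 2 weeks (Design), or after 3 weeks with 2 weeks for prescription opiates (procedures common to all three studies).
- Outcome window: last ten weeks, which is weeks 3-12 (Analysis Plan); 20 urines (Primary outcome variable(s)).
- 216 patients in all (Design), 72 of them in the prescription opioid cohort (Study Specific Background). Cocaine and marijuana together: 216 - 72 = 144.
- Alpha 0.0125 two-sided, power 80%, within-subject correlation 0.3 to 0.5 (Accrual, sample size text).

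**1. Reproduce the stated count.** Urines after the scan = 2 x (12 - scan week). For a scan after 2 weeks, 2 x 10 = 20. This matches both the stated 20 and the ten-week window.

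**2. Check which scan the 20 refers to.** If FMRI 2 in the outcome definition meant the second pre-treatment scan of the four-scan numbering, 2 x 12 = 24 urines would follow it. The figure of 20 therefore points to the on-treatment scan at 2 weeks.

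**3. Apply the 3-week timing.** 2 x (12 - 3) = 18 urines follow the scan. The fixed window still holds 20, so 20 - 18 = 2 precede it: 2/20 = 10% per patient. For opiates, 20 - 20 = 0.

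**4. Scale to the planned sample, before attrition.** 144 x 2 = 288 of 216 x 20 = 4,320 planned responses, or 6.7%.

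**5. Precision cost of using 18 urines.** Effective observations per patient are m / (1 + (m - 1) x rho).

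| rho | m = 20 | m = 18 |
|---|---|---|
| 0.3 | 20/6.7 = 2.99 | 18/6.1 = 2.95 |
| 0.5 | 20/10.5 = 1.90 | 18/9.5 = 1.89 |

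The detectable odds ratio is exp[(z for alpha 0.0125 two-sided + z for 80% power) / sqrt(N x effective observations x p(1 - p))]. With N = 216 x 0.80 = 172.8, p = 0.2 and rho = 0.3, it goes from 1.444 to 1.447. With N between 144 and 216, p of 0.2 or 0.5 and rho of 0.3 or 0.5, the change is about 0.004 at most. This takes two urines from every patient; if only two cohorts lose them, the cost is smaller still.

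**The case against.** No passage says that the 3-week text governs. If the Design section governs and scans are on schedule, nothing overlaps. The plan also lists attached procedure files, one titled for scans and the treatment phase, which may settle the timing and were not available here. This stands: the overlap is conditional. A reader might infer that pre-scan urines will certainly enter the analysis in two cohorts, and the documents do not support that.

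The effect also depends on the scan label. If the Objective 1 predictors are fMRI 1 and fMRI 2 in the four-scan numbering, both scans precede treatment and every urine follows them. That stands too, so timing and numbering have to be settled together. However, the Analysis Plan also names fMRI 3, and the hypotheses name a scan during treatment.

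Read literally, the outcome definition already restricts responses to urines after the scan. That would remove the overlap, but the 20 is then wrong for two cohorts and the ten-week window in the Analysis Plan contradicts it.

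A reader might also infer a material bias in the Objective 1 result. The documents give no figure for the effect of recent use on the scan signal, so none can be computed. Dropping two urines would also leave any association that comes from stable differences in use between patients. Nor do the documents support a larger overlap such as 4 of 20, which needs a scan one further week late; no passage describes such a delay.

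For marijuana, a positive urine need not mean recent use. The compensation section says the drug stays in the system much longer, and the saliva test entry says urine can still show earlier use. Urines after the scan can therefore reflect use before it.

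**Conclusion.** The inconsistency is real and sits in the definition of a primary outcome: for cocaine and marijuana patients, the two scan timings, the ten-week window and the count of 20 cannot all hold. If the 3-week timing is followed and the fixed window applied, 2 of 20 responses (10%) per patient, in up to 144 of 216 patients, precede the on-treatment scan. This assumes scans on schedule and a scan after both week-3 urines. It concerns only models that use the on-treatment scan; the fMRI 1 models are sound on this point under every reading. The fault is one of temporal order and of unequal windows across cohorts. It is not a loss of power, and no bias of known size has been shown.

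**What to change.** 1. Reconcile the Design section with the common procedures. The sponsor should state which scan time applies to each cohort.
2. Use one scan numbering in the Objectives, Primary outcome variable(s) and Analysis Plan, and name the scans that supply the Objective 1 predictors.
3. For models using the on-treatment scan, define the response as urines collected after each patient's actual scan date, and say whether the scan-day urine counts. Alternatively, use a common weeks 4-12 window of 9 x 2 = 18 urines in all cohorts.
4. Correct the count of 20 and the ten-week window to match.
5. State for marijuana that a urine after the scan may reflect use before it, so the cutoff restores temporal order only in part. In any cohort, the first urine after the scan may also cover some days before it, since each result refers back to the previous test.

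The cost is a change of wording plus about two correlated urines per affected patient, which moves the detectable odds ratio by about 0.004 or less. The common window would also drop two post-scan urines per opiate patient; the scan-date rule would keep them.

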Prescription Opiate Detoxification: Research study participants will have to become "clean" (detoxify) from prescription opiates prior to receiving the medication for this study. Participants may detoxify on their own, or get help with detoxification from [name] or the TRC doctors or nurses associated with this study by visiting the Treatment Research Center. At the TRC, [name] or another qualified physician or nurse appointed by [name], will provide standard supportive medical care to help participants achieve abstinence from prescription opiates, as outlined below. In addition, routine general medical care may be provided at the discretion of the study physicians, unless in the judgment of the research physician the participant should and can see their own private physician

### CURE Detox Protocol prior to Depot Naltrexone Injection

This protocol is intended only for individuals who express interest in participating in the CURE Addiction Center of Excellence: Brain Mechanisms of Relapse and Recovery Prescription Opiate study but report current use of or urine test positive for opioids.

### **Outpatient clonidine-naltrexone detoxification**

Participants who require detoxification from opioids to receive the study medication will be offered pharmacological that would follow the detoxification guidelines that have been shown to be safe and effective (Vining et al. Brit J Addiction 83, 567-575; Ockert et al. J Addict Med 5, 110-114) in this population and are in keeping with current standards of care (Tetrault & O'Connor, Management of Opioid Intoxication and Withdrawal. Principles of Addiction Medicine, 4th Edition. NY: Lippincott, 2009) along with psychological support. Dosing will follow the guidelines listed in the Handbook of Psychiatric Drug Therapy, 5th ed. (Rosenbaum JF, et al. Lippincott, 2005). Patients may be given alternative dosages within the FDA approved indication if medically necessary. As part of the signed consent procedure, individuals will sign an agreement not to drive while on this detoxification protocol. Individuals will be seen and urine toxicology done at each visit. Dosing will be based on rating on the subjective and objective severity of the withdrawal symptoms, such as anxiety, elevated blood pressure and heart rate, dilated pupils, sweating, diarrhea and muscle cramps. Individuals will be given enough medication to last them until their next scheduled visit and no more than 5 days worth. The individual will be given instructions how to contact the study clinician for any detoxification-related issues after-hours. Standard medications used will include divided doses of Clonidine, 0.1 to 1.2 mg a day, Hydroxyzine 25 to 400 mg a day, Dicyclomine 10 to 80 mg a day, Ibuprofen 400 to 2,400 mg a day, Trazodone 25 to 150 mg a day. In addition to the standard opiate detoxification protocol, oral naltrexone 50 to 100 mg a day and benzodiazepines may be prescribed to help alleviate physiological or subjective symptoms of withdrawal. The following benzodiazepines medications may be used: Lorazepam (Ativan) 0.5, 1.0, or 2.0 mg tablets every 12 hours, PRN anxiety, Oxazepam (Serax) 10, 15, or 30mg tablets every 8 hours, PRN anxiety, Clonazepam (Klonopin) 0.5, 1.0, or 2.0 mg tablets every 12 hours, PRN anxiety. Each and all of these medications are commonly used and will be prescribed by a licensed and board certified physician, guided by clinical medical need, and will not involve any experimental use. The risks and benefits of each medication will be discussed with participants before it is administered in accordance with Good Clinical Practices principles.

As part of this detoxification participants may receive oral naltrexone (50 mg per daily dose) to aid in opioid detoxification up to 1 week prior to their first depot-naltrexone injection, up to two weeks during the study as needed and up 1 week following their final scan (when their depot-naltrexone levels have declined to near zero to reduce the risk of relapse).

A Vivitrol Medical Information Card for emergency treatment will be given to all prescription opiate participants when they are given their first depot-naltrexone injection.

Since Aldermes will be providing Vivitrol (depot naltrexone) medication for the prescription opiate part of this protocol, they asked that we add the following statement to this protocol.. "If SAEs for the Vivitrol are assessed as unrelated to Vivitrol, they may be summarized on the required Quarterly Study Report that is submitted to Alkermes. If an SAE in the Vivitrol treated cohort is deemed to be a SUSAR (i.e. Serious, unexpected and is assessed as at least possibly related to Vivitrol), it should be reported to the FDA within required reporting timelines, as well as copied to Alkermes Drug Safety at the time of FDA submission. Such expedited reports may be submitted by fax to: [contact] or by email to [contact]"

CURE Pilot Project Program (separate consent): Approximately 100 separate pilot subjects will participate as part of the pilot project program using the separate pilot consent.

